In sum, there is sufficient preclinical evidence of antimicrobial effect of gNO on NTM. There are compelling reasons to use a gas for treatment as it may get to areas of the lung that will not be reached by antibiotics by either the systemic or inhalation route. Even in poorly ventilated lung units, a 50 minute exposure should be sufficient time for NO to achieve therapeutic levels. There are also sufficient safety data that the proposed exposure should be well tolerated. It is premature to predict how this therapy will be best used, but multiple options could be conceived such as eradication of first infection (especially for Mabs), improving outcomes when used in conjunction with standard antibacterial regimens, shorter durations of treatment regimens, among others. This study proposes to demonstrate that there can, indeed, be a killing effect of NTM as well as assess for how quickly it may return in sputum cultures as these will be key factors in designing subsequent treatment trials.

7 **STUDY OBJECTIVE**

The short term goal of this proposal is a proof-of-concept study in which we will expose patients with NTM lung disease and who have persistently positive sputum cultures to test the feasibility of this therapy in this population as well as the safety and efficacy of the therapy.

8 **STUDY ENDPOINTS**

- The primary measure of efficacy will be sputum culture for mycobacteria converted to negative at completion of treatment.
- Secondary measures of efficacy will include assessment of feasibility of this treatment (i.e. recruitment, completion, and satisfaction), sputum culture results for mycobacteria at 3 months following completion of treatment, and safety and tolerability assessments based on adverse events (AEs) and point of care testing for arterial oxygen saturation and methemoglobin levels.

9 **STUDY DESIGN**

9.1 **Overview of Study Design**

This open-label treatment of NTM lung disease is a proof-of-concept study to assess the efficacy of gNO in reducing the burden of NTM in patients known to have persistently positive sputum cultures. The patients will have documented NTM lung disease and meet inclusion criteria of persistently positive sputum cultures even if on antimicrobial therapy. The study is designed to evaluate the feasibility, efficacy and safety of open-label gNO in this population. Feasibility will be assessed by ease of recruitment and completion of the study, as well as a survey of the subjects' experience with the treatment and their willingness to use this as a therapy. Efficacy will be assessed by the results of sputum cultures for mycobacteria, looking at the short term effect (i.e. conversion to negative while on treatment) as well as the long-term effect (i.e. looking at the duration of culture conversion after treatment). Subjects will undergo sputum cultures at baseline and weekly during treatment, and monthly for 3 months following completion of therapy. Additional measures will include symptom scores of cough and quality of life. Safety will be assessed by monitoring of SaO₂ and metHb levels while on treatment. All serious and non-serious adverse events will be collected.

9.1.1 Screening

The investigator will review the protocol and obtain informed consent from the subjects prior to the conduct of any study procedures. There will be a review of the medical history and demographic information including underlying diagnosis. For those patients with cystic fibrosis (CF) the results of previous genetic testing will be recorded. Physical examination, including vital signs, height and weight, and pulse oximetry, will be performed. Assessment of baseline measures for efficacy will be performed (i.e. sputum collection for mycobacterial culture, cough score (Leicester), quality of life (SGRQ, CFQ-R, QOL-B).

9.1.2 Treatment Period (Days 1-15)

The treatment period is separated over 3 weeks (A, B, and C) each with 5 days of treatment, and 2 days off treatment in between. On the first day of each treatment week (A1, B1, C1) subjects will be evaluated for any changes in health or medications. They will undergo physical examination, including height and weight. They will undergo measurement of efficacy outcomes (symptom scores) as per the Study Assessment Schedule (Table 3-1). During each day of treatment (A1-A5, B1-B5, and C1-C5), subjects will be exposed to gNO through a tight-fitting mask at 160 ppm for 50 minutes for each treatment. There will be three treatments given on each day, with 3 hours between each treatment. The subjects will be monitored with pulse oximetry throughout their exposure to gNO to assess SaO₂ and metHb levels. On the last day of each treatment period (A5, B5, C5), the subjects will repeat their symptom scores as well as provide sputum for mycobacterial culture.

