MEDICAL UNIVERSITY OF SOUTH CAROLINA

Study Protocol

**A Proof of Concept Study of Inhaled Nitric Oxide for Adults
with Pulmonary Non-Tuberculous Mycobacterial Infection**

IND Number: 140649

Date and Version of Protocol: October 01, 2019

(Version 3.0)

NCT #: 03748992

IRB approved on 18SEP2018

Title	A Proof of Concept Study of Inhaled Gaseous Nitric Oxide (gNO) for Adults with Pulmonary Non-Tuberculous Mycobacterial (NTM) Infection
Clinical Phase	Phase 2
Objective	To evaluate the efficacy and safety of open-label exposure of gNO in patients with NTM lung disease
Endpoints	
Primary
 
 • Culture growth (positive or negative) at end of treatment (EOT) compared to baseline 
Secondary
 
 • Safety and tolerability assessments based on adverse events (AEs), clinical values (i.e., methemoglobin levels) • Semiquantitative mycobacterial culture results comparing EOT to baseline 
Exploratory
 
 • Time to positive mycobacterial cultures comparing EOT to baseline • Measures of systemic inflammation comparing EOT to baseline • Absolute change in quality of life scores from baseline to EOT
Study Population	Adult subjects with NTM lung disease and persistently positive mycobacterial sputum cultures
Number of Subjects	10
Number of sites	2
Study Duration	Subjects will be treated for 3 weeks (5 days per week) and followed monthly for 3 months
Study Design	This 2 study is designed to evaluate the efficacy and safety of open-label gNO treatment in subjects with NTM lung disease and persistently positive sputum cultures growing NTM. This is a proof-of-concept study in which all subjects will be treated with gNO (i.e. no control) to see if there can be a microbiological effect by conversion to negative sputum cultures and how long that effect can be sustained following treatment. In addition, this study will assess the feasibility of such a treatment course in this patient population and measure relevant clinical outcomes (e.g. cough, quality of life). Subjects will provide sputum for culture at baseline, weekly during treatment, and monthly for 3 months following treatment to assess if there is persistence of infection in cultures. Safety measures will include monitoring of arterial oxygen saturation and methemoglobin levels. All serious and non-serious adverse events will be collected

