Assessments	
 • Feasibility: ability to recruit subjects, ability to complete the planned treatment, and assessment of their experience and willingness to undergo this therapy • Efficacy: sputum cultures (mycobacteria), symptom scores (cough, quality of life) • Safety: AEs, clinical monitoring assessments (pulse oximetry), vital signs, and physical examinations
Statistical Analyses	Data will be summarized descriptively for each subject. The overall response rates (culture conversion short and long term) will be calculated after each patient has completed the trial, and exact binomial confidence intervals will be constructed.

SCHEDULE OF ASSESSMENTS

Table 3-1: Schedule of Assessments

Visit	Screening	Treatment Period									Follow up Period		
		A1	A2-4	A5	B1	B2-4	B5	C1	C1-4	C5	F1	F2	F3
Day	-28-14	1	2-4	5	8	9-11	12	15	16-18	19	W7	W11	W15
Informed consent	x												
Medical history	x												
Demographics ^a	x												
Physical examination	x	x			x			x			x	x	x
Height and weight	x				x			x			x	x	x
Vital signs	x	x	x	x	x	x	x	x	x	x	x	x	x
Symptom score ^b	x			x			x			x	x	x	x
Safety labs ^c	x									x			
CRP	x									x			
Spirometry ^d	x	x ^d			x ^d			x ^d					
Sputum cultures ^e	x			x			x			x	x	x	x
Echocardiogram	x												
Pulse oximetry	x	x	x	x	x	x	x	x	x	x	x	x	x
MetHb measurement	x	x	x	x	x	x	x	x	x	x			
gNO dosing		x	x	x	x	x	x	x	x	x			
Adverse events		x	x	x	x	x	x	x	x	x	x	x	x
Concomitant medications	x	x	x	x	x	x	x	x	x	x	x	x	x

^a Demographics include sex, race, and age. Baseline characteristics include diagnosis, and if CF include *CFTR* genotype

^b Symptom scores will include cough score (Leicester), quality of life (SGRQ, CFQ-R, QOL-B), as appropriate for the underlying diagnosis (i.e. CF subjects will complete the CFQ-R and SGRQ; other subjects will complete the QOL-B and SGRQ)

^c Safety labs include comprehensive metabolic panel (to include creatinine, AST, ALP, ALT and chemistry), complete blood cell count with differential, GGT, PT/INR, 6-GPD level, and urine pregnancy test (if applicable)

^d Spirometry will be performed pre and post first treatment of the day

^e Sputum will be tested for bacteria and mycobacteria (including AFB smear and culture). Susceptibility testing will not be performed

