14.2 Statistical Analyses

Data will be summarized descriptively for each subject. No formal comparative statistical analyses are planned

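### Section 9.1.2 can be read as placing symptom scores on A1, B1 and C1, but Table 3-1 has none there; if the table governs, the only pre-dose cough and quality-of-life score is 14-28 days before the first dose

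*Combined protocol and SAP*

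**What the plan says.** - **Section 9.1.2, first days.** The paragraph states: "On the first day of each treatment week (A1, B1, C1) subjects will be evaluated for any changes in health or medications". It goes on to physical examination with height and weight, and then: "They will undergo measurement of efficacy outcomes (symptom scores) as per the Study Assessment Schedule (Table 3-1".
- **Section 9.1.2, last days.** On A5, B5 and C5, "the subjects will repeat their symptom scores as well as provide sputum for mycobacterial culture".
- **Table 3-1.** The row "Symptom score ^b" is marked at Screening, A5, B5, C5, F1, F2 and F3. The cells for A1, B1 and C1 are blank. Section 12.1 refers to this table for all timing.
- **Section 9.1.1.** At Screening, "Assessment of baseline measures for efficacy will be performed", and the measures listed include the Leicester, SGRQ, CFQ-R and QOL-B.
- **Synopsis, Endpoints (exploratory).** "Absolute change in quality of life scores from baseline to EOT".
- **Design and analysis.** The synopsis says "all subjects will be treated with gNO (i.e. no control"; Section 14.2 says "No formal comparative statistical analyses are planned". Section 14.3.2 gives a change formula for semiquantitative cultures but does not mention the symptom scores or say which visit is baseline.

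**The concern.** The wording of 9.1.2 allows two readings. On one, subjects complete the questionnaires on A1, B1 and C1 and again at the end of each week. On the other, the sentence only points to Table 3-1, and nothing is collected on those first days. The study has two sites, and they could collect different data.

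The choice matters most at A1. Under the table, the first score after Screening comes on Day 5, after five days of gNO. The scores are self-reported, treatment is open-label and there is no control, so change from baseline carries the symptom result. Section 9.2 counts symptom-based efficacy among the key measures. If a subject's cough or quality of life shifts between Screening and Day 1, that shift becomes part of the change reported at EOT, and the data cannot show that it happened before treatment.

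**Working it through.** The plan states no figure on this point to reproduce. The check is a reading of the table row and a count of days.

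**1. Table row.** Table 3-1 has 13 visit columns. In the symptom-score row, 7 are marked: Screening, A5, B5, C5, F1, F2, F3. Six are blank, including A1, B1 and C1.

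**2. Are text and table otherwise aligned?** Not fully. The same part of 9.1.2 puts height and weight on the first day of each week, including A1. Table 3-1 marks them at Screening, B1, C1 and F1-F3, but not at A1. This makes a drafting mismatch plausible for the symptom scores too.

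**3. Inputs for the day count (Table 3-1).** Screening is Day -28 to Day -14 (the window is printed without a separator and is read this way). A1 is Day 1 and C5 is Day 19. EOT is taken as C5, the last treatment day. No Day 0 is assumed.

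**4. Intervals.**

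| | Screening at Day -28 | Screening at Day -14 |
|---|---|---|
| Screening to first dose | 28 days | 14 days |
| First dose to EOT (19 - 1) | 18 days | 18 days |
| Baseline to EOT | 28 + 18 = 46 days | 14 + 18 = 32 days |
| Untreated share | 28/46 = 61% | 14/32 = 44% |

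If a Day 0 is counted, the untreated interval is 15-29 days, the total 33-47 days, and the share 15/33 = 45% to 29/47 = 62%. The conclusion does not depend on this convention.

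**5. What the change score contains.** For any one subject,

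score at EOT - score at Screening = (score at EOT - score at Day 1) + (score at Day 1 - score at Screening).

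The second bracket is change before any gNO. Under Table 3-1 there is no Day 1 score, so only the sum is observed. With a pre-dose A1 score both brackets are observed, the baseline-to-EOT interval is 18 days, and its pre-dose part is 0.

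**6. Do other provisions cover the gap?** Section 10.1 requires stability over the 14 days before Screening or Day 1. If Day 1 is the anchor, that covers 14 of 14 days for the latest Screening and 14 of 28 for the earliest. If Screening is the anchor, it covers none. In either case it concerns health status and yields no score. The Section 10.2 limits on new chronic therapy and on steroids look back from Screening, not forward to Day 1.

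**The case against.** The strongest reply is that there is no contradiction. The 9.1.2 sentence names no day itself and defers to Table 3-1, as does Section 12.1. Section 9.1.3 uses almost the same sentence for follow-up. A repeat on A5 can mean repeating the Screening score, and 9.1.1 names Screening as the efficacy baseline outright, so this looks like a choice and not an oversight. Most of this stands. A reader might infer that 9.1.2 firmly orders scores on A1, B1 and C1; the deferral to the table does not support that. But the reply settles the ambiguity in favour of the table, which is the reading that leaves no score on Day 1.

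A second reply is that drift is asserted, not shown. This also stands. A reader might infer that untreated drift is being counted as a gNO effect, or that 44%-61% of the reported change is spurious. The documents give neither size nor direction of any drift, and the eligibility criteria and the A1 health review may keep it small. The weekly and monthly scores give a time course, but every one of them follows the first dose and so cannot show what happened before it.

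A reader might also extend the mismatch to sputum culture and CRP, since each is taken at Screening and not again before dosing. The documents do not support that. Sections 9.1.2 and 12.4.1 agree with Table 3-1 on when sputum is taken, and no text places CRP on A1. Re-baselining only some culture endpoints could also create two culture baselines.

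**Conclusion.** The point holds as a wording mismatch with a real but bounded consequence. Section 9.1.2 and Table 3-1 should be reconciled. If the table governs, the sole pre-dose cough and quality-of-life score precedes the first dose by 14-28 days, and the design offers no way to separate change in that interval from change on gNO. The 44%-61% is a share of calendar time; the bias could be nil or could run in either direction.

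This rests on reading the screening window as Day -28 to -14 and on EOT being C5 at Day 19. If 9.1.2 governs instead, an A1 score exists, but nothing says it comes before the first inhalation.

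The quality-of-life endpoint is exploratory and the analysis descriptive, so no sample size, error rate or primary culture result is affected. The change is still worth making, because it is cheap and cannot be recovered after enrolment.

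**What to change.** 1. In Table 3-1, add a symptom score at A1, stated to be completed before the first inhalation.
2. Define that score as the baseline for the cough and quality-of-life changes, and amend 9.1.1 so that it no longer gives Screening that role for these scores.
3. Keep the Screening score, and report Screening-to-A1 change beside A1-to-EOT change so that pre-treatment drift is visible.
4. Correct the 9.1.2 wording for B1 and C1 to match the table, which has no score on those days.

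The sputum and CRP schedules stay as they are.

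**Cost.** Subjects already attend A1. The addition is one set of three questionnaires each (Leicester, SGRQ, and CFQ-R or QOL-B), at most 10 × 3 = 30 forms, plus small edits to Table 3-1, 9.1.1 and 9.1.2.

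**Limit.** An A1 baseline removes only the pre-dose interval. Drift over the 18 days from A1 to EOT and expectation effects from open-label treatment remain.

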9.1.3 Follow Up Period (3 months)

Patients will be evaluated monthly for 3 months for any changes in health or medications. They will undergo physical examination, including height and weight. They will undergo measurement of efficacy outcomes (symptom scores, sputum cultures) as per the Study Assessment Schedule (Table 3-1).

9.2 Rationale for Study Design

This is a proof-of-concept study based upon *in vitro* exposure of NTM to gNO. The primary efficacy measure (conversion to negative mycobacterial cultures) are expected to change in the short term (i.e. during the 3 week treatment period), but assessment after completion of treatment is important to determine if there is a return to culture positivity in the immediate term post-treatment. The overall culture response rate and the time to recurrence (if it recurs) will be important data to determine if this therapy has clinical potential for this patient population and the resulting data will be helpful for estimating the effect size to be used in designing a future randomized controlled trial

The other key measures include reduction in the mycobacterial density (in the event that cultures do not convert to negative, this will provide information about some treatment effect), efficacy based on symptoms, safety, and the feasibility of conducting a larger trial or whether this therapeutic regimen would have viability.

As this is a proof-of-concept study, there is no value to a blinded aspect for the study.

NO-NTM

Treatment will be open-label and clinical outcomes will be assessed by the individuals.

10 SELECTION OF STUDY POPULATION

10.1 Inclusion Criteria

Patients with NTM lung disease who persistently demonstrate infection with positive sputum cultures will be eligible for the study. This will include patients with and without CF as this is typical of the NTM population and this therapy should be non-discriminatory. Inclusion criteria are as follows:

- Subjects are ≥ 18 years of age and able to provide informed consent.
- Subjects have NTM lung disease as defined by each of the following:
 - Sputum cultures positive for NTM (MAC or *M. abscessus*)
 - Radiologic studies that demonstrate features consistent with disease such as nodular bronchiectasis and/or cavities
 - Symptoms consistent with disease including respiratory (e.g. cough, sputum production, hemoptysis, chest pain) and constitutional (e.g. fevers, night sweats, fatigue, myalgias, arthralgias, weight loss)
- Subjects are able to produce sputum for culture (either spontaneous or induced).
- Subjects have a history of persistently positive sputum cultures for NTM defined as
 - ≥ 2 positive cultures over the preceding 6 months AND
 - Has not met the definition for culture clearance in the last 6 months (three negatives in a row)
- Clinically stable with no significant changes in health status within 14 days prior to Screening or Day 1
- Subjects are willing and able to perform requirements of the study.

Appendix: Guidance for eligibility based on definition of persistent infection

The definition of persistent infection in the inclusion criteria is:

- Subjects are able to produce sputum for culture (either spontaneous or induced).
- Subjects have a history of persistently positive sputum cultures for NTM defined as:
 - ≥ 2 positive cultures over the preceding 6 months AND
 - Has not met the definition for culture clearance in the last 6 months (three negatives in a row).

Since there will be heterogeneity in culture frequency, this table will assist in defining eligibility:

Samples taken	Samples found to have NTM (positive samples)						
	0	1	2	3	4	5	6
2	0/2	1/2	2/2	--	--	--	--
3	0/3	1/3	2/3	3/3	--	--	--
4	0/4	1/4	2/4	3/4	4/4	--	--
5	0/5	1/5	2/5	3/5	4/5	5/5	--
6	0/6	1/6	2/6	3/6	4/6	5/6	6/6

Red = not eligible

Green = eligible

Yellow = potentially eligible (depending on whether culture conversion definition is met)

The definition of culture conversion is at least 3 consecutive negative mycobacterial cultures from respiratory samples, collected at least 4 weeks apart (i.e. no intervening positives). The table below demonstrates the varying possibilities for the potentially eligible subjects from the table above.

Number positives	Months prior to screening							Eligible
	6	5	4	3	2	1	0	
2	X	O	X	O	O	O	.	No
2	O	X	X	O	O	O	.	No
2	X	X	O	O	O	O	.	No
2	O	X	O	O	O	X	.	No
2	X	O	O	O	O	X	.	No

NO-NTM

2	X	O	O	O	X	O	.	No
2	O	O	O	O	X	X	.	No
2	O	O	O	X	X	O	.	No
2	O	O	O	X	O	X	.	No
3	X	X	X	O	O	O	.	No
3	X	X	O	O	O	X	.	No
3	X	O	O	O	X	X	.	No
3	O	O	O	X	X	X	.	No
2	X	O	O	X	O	O	X	Yes
2	O	X	O	X	O	O	X	Yes
2	O	X	O	O	X	O	X	Yes
2	O	O	X	X	O	O	X	Yes
2	O	O	X	O	X	O	X	Yes
2	O	O	X	O	O	X	X	Yes

For those deemed ineligible, they may yet become eligible. In the following table, are different scenarios in which could be rescreened or become eligible within a period of time. S2, S3 and S4 indicate that the participant should be screened again after 2, 3, or 4 months. For these participants, no more than one positive culture has occurred since meeting the definition for culture conversion, and more positive cultures will need to occur to meet eligibility requirements. E1 and E2 indicate that the participant will be eligible after 1 or 2 months. For these persons, two qualifying, positive cultures have occurred since evidence of culture conversion.

Number positives	Months prior to screening							
	6	5	4	3	2	1	0	
2	X	O	X	O	O	O		S4
2	O	X	X	O	O	O		S4
2	X	X	O	O	O	O		S4
2	O	X	O	O	O		X	S3
2	X	O	O	O	O		X	S3
2	X	O	O	O		X	O	S2
2	O	O	O	O		X	X	E2
2	O	O	O		X	X	O	E1
2	O	O	O		X	O	X	E1
3	X	X	X	O	O	O		S4
3	X	X	O	O	O		X	S3
3	X	O	O	O		X	X	E2
3	O	O	O	X	X	X		E1

10.2 Exclusion Criteria

Subjects will be excluded if they have any of the following:

- Smoking history in the prior 6 months
- Significant hemoptysis within 30 days prior to screening (>5 ml of blood in one coughing episode or >30 ml of blood in a 24 hour period)
- Forced expiratory volume at one second (FEV₁) <40% of predicted
- On supplemental oxygen or SaO₂ <90% at screening or Day 1, or within 30 days prior to enrollment.
- Known cardiac (left heart) insufficiency (defined as LVEF <35%) prior to screening
- Known pulmonary hypertension
- Known or suspected hemoglobinopathy
- Initiation of NTM treatment regimen or a change in the regimen was made in the prior 6 months. Subjects on active treatment can be enrolled if they have been on a stable anti-NTM regimen for at least 6 months.
- Initiation of new chronic therapy within 4 weeks prior to screening
- Use of drugs known to increase methemoglobin (see 12.2.7) at screening
- Any of the following abnormal lab values at screening:
 - 6-GPD deficiency
 - Hemoglobin <10g/dl
 - Platelet count <100,000/mm³
 - Prothrombin time international ratio (INR) >1.5
 - Abnormal liver function defined as any two of the following
 - ALT >3x ULN
 - AST >3x ULN
 - ALP >3x ULN
 - GGT >3x ULN
 - Abnormal renal function defined as:
 - Calculated Creatinine Clearance <50 ml (as calculated by Cockcroft/Gault)
- For women of child bearing potential:
 - Positive pregnancy test at screening or
 - Lactating or
 - Unwilling to practice a medically acceptable form of contraception from screening to Day 15 (acceptable forms of contraception: abstinence, hormonal birth control, intrauterine device, or barrier method plus a spermicidal agent)
- Use of an investigational drug within 30 days prior to screening
- Intravenous or oral steroids (>10 mg/d prednisone equivalent) in the 14 days prior to screening
- Any condition that the Investigator believes would interfere with the intent of this study or would make participation not in the best interest of the subject.

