11 DOSING OF STUDY DRUG

11.1 General Dosing Information

Gaseous NO (5000 ppm), delivered with air as carrier to dilute it to 160 ppm, will be administered by inhalation for 50 minutes three times daily on Days 1-5, 8-12, and 15-19. On each day, treatment will be given with a minimum of 3 hours between the end of one treatment and the start of the following treatment. Subjects will receive 160 ppm during each 50 minute inhalation period (daily exposure 400 ppm hours). This will result in a total of 6000 ppm hours of exposure.

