Sputum will be collected for culture at Screening, and Days 5, 12, and 19 (treatment dates), and Weeks 7, 11 and 15 (follow up). Sputum samples will be processed at the MUSC clinical laboratory, using standard decontamination procedures, fluorochrome microscopy, solid medium culture on a biplate of Middlebrook 7H10 agar with and without antibiotics, and a broth culture (BACTEC 960 [Becton Dickinson, Sparks, MD] or ESP [TREK Diagnostic Systems, Cleveland, OH]). MAC isolates are identified with AccuProbe (Hologic-GenProbe, San Diego, CA).

Semiquantitative AFB smear and culture results for each submitted clinical specimen will be recorded [Wallace 1996]. Briefly, a negative culture exhibits no mycobacterial growth. Cultures will be reported as positive if growth occurs in broth medium only; growth on broth medium plus solid medium cultures with countable colonies will be reported as 0–49 colonies, 1+; solid medium growth with 50–99 colonies, 2+; solid medium growth with 100–199 colonies; 3+, solid medium growth with 200–299 colonies; and 4+, solid medium growth with at least 300 colonies. For data analysis, each culture will be scored as follows: 0, no growth in broth or solid medium; 1, broth medium growth only; 2, countable colonies (<50 colonies) on solid medium; and 3–6, 1+ to 4+ growth on solid medium, respectively.

12.5.1**Quality of life measures**

Validated instruments will be used for measurement of symptoms and quality of life. Since study subjects may have different underlying conditions, for which there are different quality of life measures, we will use a condition specific measure for each as follows:

NO-NTM

- Cystic fibrosis: Cystic fibrosis Questionnaire-Revised (CFQ-R)
- Bronchiectasis: Quality of Life – Bronchiectasis (QOL-B)
- All: St. George's Respiratory Questionnaire (SGR-Q)
- All: Leicester Cough Score

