14.1 Sample Size and Power

Planned enrollment is a minimum of 6 and a maximum of 10 subjects in this study. If a high enough proportion of subjects demonstrate a response (e.g. 5 of 6 or 6 of 8) early on in the trial, we may be able to limit the sample size, since the 95% confidence intervals would indicate a high certainty that this therapy is worth pursuing in a larger randomized controlled trial. If, however, none of the 10 subjects exhibit a response, then we can be almost certain that this particular therapy is futile, since the resulting 95% confidence interval around the response rate would range from 0% to 31%.

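### The contraception criterion stops at Day 15, the first day of the last treatment week on the protocol's calendar, while dosing runs to Day 19

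*Combined protocol and SAP*

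**What the plan says.** For women of child-bearing potential, section 10.2 lists as a reason for exclusion: "Unwilling to practice a medically acceptable form of contraception from screening to Day 15".

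Four other places fix the treatment calendar:

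- Section 11.1: gNO "will be administered by inhalation for 50 minutes three times daily on Days 1-5, 8-12, and 15-19".
- Table 3-1: the day row reads "Day -28-14 1 2-4 5 8 9-11 12 15 16-18 19 W7 W11 W15". C1 sits on Day 15, the next column on Days 16-18 and C5 on Day 19, and gNO dosing is marked in all three.
- Section 12.4.1: "Sputum will be collected for culture at Screening, and Days 5, 12, and 19 (treatment dates"; Day 19 is therefore a dosing day.
- Section 9.1.2: the heading is "Treatment Period (Days 1-15", but the text beneath describes three weeks, "each with 5 days of treatment, and 2 days off treatment in between".

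No other section mentions or extends the contraception period.

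**The concern.** An eligibility criterion of this kind is there to prevent pregnancy while a subject is receiving an investigational drug, so it should cover at least every dosing day. On the day numbering used for dosing, visits and sputum collection, this one ends with four dosing days still to come. A woman could satisfy it by agreeing to contraception only through the first day of the final treatment week.

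The probable origin is a day-count slip. There are 15 dosing days, but they are spread over 19 calendar days, and the heading of 9.1.2 appears to make the same slip. Two sites have to apply the eligibility list, and both need one unambiguous end day. What is at stake is participant protection. The trial's inference is not touched.

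**Working it through.** **Inputs**

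- Contraception window: screening to Day 15 (10.2).
- Dosing days: 1-5, 8-12 and 15-19, with three inhalations a day of 50 minutes at 160 ppm (11.1).
- Stated exposure: 400 ppm-hours a day and 6,000 in total (11.1).
- Pattern: 5 days on, 2 days off, over three weeks (9.1.2 text).
- Enrolment: 6 to 10 subjects (14.1).

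**Step 1. Reproduce the plan's own exposure figures**

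- Daily: 160 ppm × 50/60 h × 3 = 400 ppm-hours.
- Dosing days: 5 + 5 + 5 = 15.
- Total: 15 × 400 = 6,000 ppm-hours.

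Both stated figures are reproduced exactly, so the course is 15 dosing days and 15 × 3 = 45 inhalations.

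**Step 2. Find the last dosing day from the text of 9.1.2**

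5 + 2 + 5 + 2 + 5 = 19 calendar days. This agrees with 11.1, Table 3-1 and 12.4.1, and disagrees with the section's own heading.

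**Step 3. Locate Day 15**

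On the calendar, Day 15 is C1, which is dosing day 5 + 5 + 1 = 11 of 15. Dosing remains on Days 16, 17, 18 and 19.

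**Step 4. Count what falls after the window under each reading**

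| Reading of Day 15 | Dosing days after window | Inhalations | ppm-hours |
|---|---|---|---|
| Calendar day (11.1, 12.4.1, Table 3-1) | 4 of 15 | 4 × 3 = 12 of 45 | 4 × 400 = 1,600 of 6,000 (26.7%) |
| Fifteenth dosing day (= calendar Day 19) | 0 | 0 | 0 |

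**Step 5. Number of women affected**

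The documents do not say how many subjects would be women of child-bearing potential. Section 14.1 states: "Planned enrollment is a minimum of 6 and a maximum of 10 subjects in this study". The possible range is therefore 0 to 10.

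**The case against.** The strongest reply is that no gap was intended. The heading of 9.1.2 labels the whole course, A1 to C5, as Days 1-15, and 10.2 uses the same end day. The natural inference is that the author meant the end of treatment. Table 3-1 supports this: safety labs, which include a urine pregnancy test where applicable, are marked at Screening and at C5, so pregnancy precautions do run to the last dosing day. The criterion also screens for unwillingness at entry and does not tell anyone to stop contraception on Day 15. A woman using an intrauterine device or hormonal method would hardly stop mid-course because of this wording. Finally, ppm-hours after a date measure exposure, not the chance of an exposed pregnancy, and the documents give no reproductive-toxicity information from which to judge four days' consequence.

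Much of this stands as a limit on the size of the problem. Intent to cover the whole course is likely, the practical gap is mainly for subjects relying on abstinence or barrier methods, and the 27% is a share of dosing, not a risk.

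It does not remove the defect. Section 10.2 does not say that it counts dosing days, and nothing in the protocol defines such a count. Under the benign reading, Day 15 means C1 in the schedule and C5 in the eligibility list. A pregnancy test on Day 19 does not require contraception on Days 16-19, and it could not be relied on to detect a conception in those days. What subjects were told in the consent form cannot be judged from these documents.

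**Conclusion.** The concern holds. As written, and on the numbering used in 11.1, 12.4.1 and Table 3-1, the required contraception period ends four dosing days before treatment does. The size given rests on reading Day 15 as a calendar day. That is the more natural reading, but it is not the only one: if dosing days were meant, the text is ambiguous and no dosing is left uncovered. Either way 10.2 needs a clear end day.

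This should be fixed because it is an operative eligibility rule protecting participants. It has no bearing on the endpoints, the sample size or the analysis.

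**What to change.** - In 10.2, replace Day 15 with Day 19 (last dose of gNO) as the minimum. Any margin after the last dose is for the sponsor to decide.
- In the 9.1.2 heading, replace Days 1-15 with Days 1-19.
- Align the consent wording if it repeats Day 15.

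The cost is two one-line protocol corrections, plus the consent text if needed. No visit, test or subject is added.
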